## 1.0 Objectives\*

1.1 The purpose of this study is to determine if activation training of the hip musculature affects muscle activation and frontal plane mechanics in healthy individuals.

Specific Aim 1: Determine whether performance on the forward step-down test (FSDT) changes after an eight-week home exercise program (HEP) focused on hip musculature activation in healthy individuals.

Specific Aim 2: Determine whether surface electromyography (sEMG) hip musculature changes following an eight-week HEP focused on hip musculature activation in healthy individuals.

Specific Aim 3: Determine whether a dose-response relationship exists between compliance on the HEP and changes in FSDT scores in healthy individuals.

Specific Aim 4: Determine whether a dose-response relationship exists between compliance on the HEP and sEMG changes in hip musculature activation in healthy individuals.

1.2 Specific Aim 1:

$H_0$ : There will be no significant change in FSDT scores after an eight-week hip musculature activation HEP in healthy individuals.

$H_1$ : There will be a significant change in FSDT scores after an eight-week hip musculature activation HEP in healthy individuals.

Specific Aim 2:

$H_0$ : There will be no significant change in sEMG data of hip musculature after an eight-week hip musculature activation HEP in healthy individuals.

$H_1$ : There will be a significant change in sEMG data of hip musculature after an eight-week hip musculature activation HEP in healthy individuals.

Specific Aim 3:

$H_0$ : There will be no significant dose-response relationship between HEP compliance and FSDT scores in healthy individuals.

$H_1$ : There will be a significant dose-response relationship between HEP compliance and the FSDT scores in healthy individuals.

Specific Aim 4:

H0: There will be no significant dose-response relationship between HEP compliance and sEMG data of hip musculature in healthy individuals.

H1: There will be a significant dose-response relationship between HEP compliance and sEMG data of hip musculature in healthy individuals.

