### **3.0 Inclusion and Exclusion Criteria\***

- 3.1 Screening will be done concurrently with the written informed consent process through a self-reported assessment.
- 3.2 Inclusion: Participants must be current first or second year Doctor of Physical Therapy (DPT) students in the School of Allied Health Professions (SAHP) at LSU Health Shreveport (LSUHS).  
Exclusion: current knee pain or pathology in the dominant leg, and women with known pregnancy.
- 3.3 Regarding the inclusion of persons at increased risk:
  - Adults unable to consent: excluded due to not meeting inclusion criteria
  - Individuals who are not yet adults (infants, children, teenagers): excluded because this is not our target population
  - Pregnant women: excluded due to creating greater than minimal risk
  - Prisoners: excluded due to not meeting our inclusion criteria

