## **9.0 Procedures Involved\***

- 9.1 The study will utilize a repeated-measures design, where all participants will perform the FSDT for assessment pre- and post-intervention via an HEP while sEMG data is being collected from the gluteus medius and gluteus maximus. All of the activities listed above will be performed on the dominant LE. The HEP will be a combination of hip musculature activation exercises used by previous researchers that show an increase in hip muscle recruitment. Core activation via a side plank will be added to the clam exercise and the side-lying hip abduction exercise. In this design the dependent variables are the scores on the FSDT pre- and post-HEP, sEMG pre-and post-HEP, and compliance with the HEP. The independent variable is the performance of the eight-week HEP. Two physical therapist students will perform the FSDT assessments and sEMG data collection (CH and MS). Two faculty members will also assist with data collection (DF and EM). Prior to data collection and assessments, the two students (CH and MS) will be educated by the primary investigator (DF), who is a board-certified orthopedic clinical specialist physical therapist with ten years of experience, on the FSDT protocol. Scoring guidelines of the FSDT will be reviewed according to the study by Park *et al* and practiced prior to data collection. The sEMG electrode placement will come from *The ABC of EMG*. The procedure for collection of the maximum volitional isometric contraction (MVIC) of the gluteus medius will follow the protocol used in a study by Harput *et al*. The MVIC of the gluteus maximus will follow the protocol used in a study by Selkowitz *et al*, with the knee flexed to 90° in prone. The same methodology will be used from [name] and [name] for scoring and reporting of the FSDT scores.

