to attend an initial data collection session in the rehabilitation faculty clinic and the motion analysis lab 2-217 in the SAHP at LSUHS. Participants will meet in the rehabilitation faculty clinic and age, sex, height, weight, BMI, and dominant lower extremity (LE) will be recorded by DF or EM. The dominant LE is defined as the leg that they usually use to kick a soccer ball. Participants will take the elevator to the second floor and report to 2-217 for sEMG and FSDT data collection. During this time, sEMG electrodes will be applied to the gluteus maximus and medius of the dominant leg, following the placement criteria from *The ABC of EMG* by EM (for female participants) or DF (for male participants) and an MVIC for each muscle will be performed and recorded, with resistance by CH. Participants will be instructed on the procedure for the FSDT by CH prior to completing the test. The FSDT consists of five consecutive repetitions of a forward step down from a 20cm step, with one score given for the whole set of five repetitions. The two student investigators (CH and MS) will both score and average the number between the two scores. sEMG data and FSDT scores will be collected before and after the 8 week HEP. After the initial FSDT is completed, the participant will be educated on the HEP and the compliance chart by MS. The HEP will be a combination of hip musculature activation exercises used by previous researchers that show an increase in hip muscle recruitment. Core activation via a side plank will be added to the clam exercise and the side-lying hip abduction exercise. The HEP consists of five hip activation exercises, clams, clams with trunk activation via side-plank, side-lying hip abduction, side-lying hip abduction with trunk activation via side-plank, and hydrants. The participants will perform isometric contractions of these exercises for up to one minute on the LE used for testing. Once the participant is able to hold all of these exercises for one minute without a break, the participant will advance to the next step, adding a yellow theraband and completing the same exercises. If the participant is able to isometrically hold these five exercises for one minute with a yellow theraband, the participant will progress to a red theraband and repeat the process of working towards one minute holds of each exercise. Each participant will demonstrate the exercises of the HEP to ensure proper form and be informed on the proper progression of the exercises. A compliance chart will be given to the participants to track every time they perform the HEP. Previous authors have used compliance charts to measure this variable in preparation for a dose-response analysis for activation programs. The participants will take home their HEP, a compliance chart, and a yellow and red theraband. The participants will complete the HEP two days a week for eight weeks, with at least two rest days between sessions, and document the completion of the session on the compliance chart. At the end of the 8 week period,

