
each participant will be scheduled to return to the motion analysis lab to turn in their compliance sheet and perform a follow-up sEMG and FSDT using the same procedures as before.

9.3 Table of events that lists each procedure or test and how often the procedure or test will occur:

Written informed consent	1
Eligibility screening	1
Anthropometric assessment (height, weight, BMI)	1
FSDT	2
sEMG	2
HEP education	1
Compliance chart education	1
HEP	16
Compliance chart documentation	16

9.4 To reduce the risk of loss of confidentiality, participants will be assigned numbers. All hardcopy data will be stored in DF office (locked), room 2-234 in the SAHP at LSUHS in a locked drawer. All electronic data will be stored using Sharepoint connected to school email addresses with a password.

To reduce the risk of muscle soreness, participants will be educated on proper performance of the exercises, to space sessions at least two days apart, and to add a band or progress to a yellow theraband once they can perform all exercises for one consecutive minute on the dominant LE. An informed consent document with participant identification numbers will be used to obtain consent from the participants. A participant identification number key will be made to match the participant name to their assigned number to maintain confidentiality. A sign up for the anthropometric data collection and pre- and post-HEP sEMG and FSDT data collection will be created, allowing the participants to sign up with their identification number. An excel sheet to collect data will be used by the investigators. A compliance chart for the participants to track their exercise sessions will be created. A paper copy of the HEP will be given to the participants.

9.5 Data collected will consist of participant age, height, weight, BMI, all at the first visit, in addition to the following pre- and post-intervention: FSDT, sEMG from gluteus medius and maximus, recorded FSDT video. The data from the compliance chart will only be collected post-intervention.

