11.3 See 9.4

11.4 The student investigators (CH and MS) will be educated on the proper procedures of the FSDT, sEMG data collection, and the HEP by the primary investigator (DF) and co-investigator (EM). The FSDT will be analyzed and scored by the two student investigators (CH and MS). The student investigators (CH and MS) will record and average their scores following the completion of five repetitions to improve the quality of the data. The sEMG electrodes will be placed on the female participants by EM and on the male participants by DF. CH will provide the pressure for the MVIC and explain the FSDT procedure to every participant. MS will explain the HEP and the compliance chart to the participants. The primary investigator (DF) is a board-certified orthopedic physical therapist with 10 years of experience, who has published research on this test. The co-investigator (EM) is also a board-certified orthopedic physical therapist with 5 years of experience, who also published research on this test with the primary investigator.

11.5 The data that will be collected during the entire study includes: participant number, height, weight, BMI, sex, leg dominance, FSDT pre and post HEP, recorded FSDT video, sEMG from gluteus medius and maximus on the dominant leg during FSDT pre and post HEP, and compliance. Data storage will follow the guidelines in section 9.4. The data will be stored for the duration of the study and throughout the following semester while analyzing and finalizing data for presentation. The data will be kept up to one year after the completion of the data analysis in event that the research wants to be continued. The only people to have access to this information will be the primary investigators, student investigators, and the co-investigator (DF, EM, CH, MS). All investigators are responsible for the receipt and transmission of the data. Data will be manually transported to DF office room 2-234 in the SAHP at LSUHS. Electronic data will remain on Sharepoint.

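### Other hip, core and leg training is neither held stable nor recorded, so it could bias the compliance-outcome relation in Aims 3 and 4

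*Combined protocol and SAP*

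**What the plan says.** The design is a single group measured twice (Section 9.1): "The study will utilize a repeated-measures design, where all participants will perform the FSDT for assessment pre- and post-intervention via an HEP". There is no comparison arm.

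The places where outside training could have been limited or recorded are these:

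- **Eligibility (3.2).** The exclusions are "Exclusion: current knee pain or pathology in the dominant leg, and women with known pregnancy". Current training is not mentioned.
- **Exercise instructions (9.2).** "The participants will complete the HEP two days a week for eight weeks, with at least two rest days between sessions". The spacing rule here and in 9.4 concerns the study's own sessions.
- **Compliance chart (9.2).** "A compliance chart will be given to the participants to track every time they perform the HEP". Section 9.4 describes the chart more loosely as a log of exercise, but 9.2 ties it to the home exercise programme (HEP).
- **Table of events (9.3).** No entry concerns other physical activity.
- **Data lists (9.5 and 11.5).** The first opens "Data collected will consist of participant age, height, weight, BMI, all at the first visit" and the second "The data that will be collected during the entire study includes: participant number, height, weight, BMI, sex, leg dominance, FSDT pre and post HEP". Neither goes on to name other exercise.

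Aim 3 is to "Determine whether a dose-response relationship exists between compliance on the HEP and changes in FSDT scores in healthy individuals", and Aim 4 asks the same of sEMG. Section 11.1 specifies paired tests for the pre-post comparisons. It names no method for Aims 3 and 4, so no adjustment for other activity is planned.

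**The concern.** Aims 3 and 4 compare participants with one another: do those who complete more sessions change more? A student who is keen on exercise may complete more HEP sessions and also do more other training. If that training affects the step-down score or gluteal activation, compliance will correlate with change even if the HEP does nothing. The link can also run the other way. A student with a full training schedule may skip HEP sessions, and a real dose-response would then be weakened or hidden. Neither a control arm nor cautious causal wording for Aims 1 and 2 would remove this, because the bias arises between participants who all receive the HEP.

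The plan's own rationale makes the route plausible. Section 2.1 reports that adding core activation to hip exercises raised lower-limb muscle activation, and it frames the open question as what hip activation training does by itself. That question is hard to answer if other hip, core and leg work is neither held steady nor measured.

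For Aims 1 and 2 the risk is narrower: a net movement in outside training across the cohort between the two tests would be counted as part of the pre-post change.

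**Working it through.** **Number of completers.** Section 11.2 gives r = .27, d = .56, two-sided alpha .05, 80% power, N = 29, 20% attrition and 35 recruited.

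- d = 2r/√(1 − r²) = .54/√.9271 = .561, which agrees with the plan.
- At d = .56 a paired t-test needs 28. A signed-rank test with asymptotic relative efficiency 3/π needs 29, so the plan's 29 reproduces.
- 29 × 1.20 = 34.8, giving 35. A 20% loss from 35 leaves 35 × .80 = 28 completers, the n used below.

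The sample size is not in dispute here.

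**Size of the study exposure.** At most 10 minutes a session (7.1) and 16 sessions (9.3): 16 × 10 = 160 minutes over eight weeks. The documents give no figure for other training.

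**Aims 3 and 4.** Let C be compliance, E outside training and Y outcome change (scored so that higher is better), all standardised, with Y = βC + γE + error and corr(C, E) = r1. Then

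corr(C, Y) = β + γ·r1.

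With no HEP effect, β = 0 and γ equals r2 = corr(E, Y), so the induced correlation is r1 × r2. The values of r1 and r2 are assumptions. Rejection rates are for a two-sided Pearson test at .05, by simulation with 40,000 runs per row:

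| r1 = r2 | induced correlation | rejection, n = 28 | rejection, n = 29 |
|---|---|---|---|
| .2 | .04 | 5.5% | 5.4% |
| .3 | .09 | 7.5% | 7.3% |
| .4 | .16 | 12.6% | 13.2% |
| .5 | .25 | 25.6% | 26.0% |
| .6 | .36 | 48.1% | 49.8% |

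A separate run at n = 28 gave 7.4%, 12.8%, 25.1% and 48.7% for the last four rows. The rounded figures are therefore about 5%, 7%, 13%, 25% and 49%. They are for a Pearson test and serve as an approximation for a rank correlation.

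*Masking.* If r1 is negative, the second term subtracts. For example, β = .16, γ = .4 and r1 = −.4 give .16 + (.4 × −.4) = 0, so a real relation disappears. With β = 0 and r1 negative, the rejection rates are those in the table, but the apparent relation is inverse.

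**Aims 1 and 2.** If the HEP has no effect but outside training shifts the mean change by b standard deviations of the change score, a paired t-test has noncentrality b√n. At n = 28 the rejection rate is 8.0%, 17.5%, 33.4% or 53.2% for b = .1, .2, .3 or .4. These b values are also assumptions. If habitual training is constant and no longer taking effect, it need contribute nothing (b = 0).

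**The case against.** The strongest reply is that much of this depends on what the documents do not say. Several stronger readings that a reader might infer go too far.

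- **That participants are free to do any other training.** The documents neither allow nor forbid it. The consent form (28.3) is attached separately, and the paper HEP handout and chart (9.4) are not in the visible text. An instruction could sit there.
- **That the data lists are closed, so the information can never be recovered.** Section 11.5 says only what the data include and omits age, which 9.5 collects. Section 9.5 omits sex and leg dominance, which 9.2 and 11.5 record. Investigators could also ask at the week-8 visit. What stands is that nothing plans for this.
- **That a gym programme would produce more change than the HEP could.** No figure in the documents gives the effect of either. Section 2.1 reports that strength training did not change movement in women with patellofemoral pain. That is a different population and does not address sEMG, but it does not support the inference. Comparing minutes of general training with minutes of targeted activation would not compare like with like.
- **That any outside training inflates the pre-post change.** Stable training need not. One student starting and another stopping mainly adds noise. A false mean change needs a net shift in one direction.

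The dose-response bias is also negligible when both links are weak. None of this removes the gap: followed as written in the visible text, the plan cannot separate HEP compliance from outside training in Aims 3 and 4.

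**Conclusion.** The point holds as a design gap in the visible text. Other hip, core and lower-limb training is not asked to be kept stable and is not recorded at baseline or during the eight weeks. It could bias the compliance-outcome relation in either direction, and a net cohort shift could add to the pre-post change.

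Its size is uncertain. With no HEP effect and 28 completers, the false-positive rate runs from about 5% (both correlations .2) through 7%, 13% and 25% to 49% (both .6). The documents support no particular value in that range. A reader might infer that a significant dose-response would come entirely from outside training, but no figure shows that. The supported statement is that such a result could not be told apart from one caused, in part or whole, by outside training. The planned sample size is unaffected.

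**What to change.** 1. At the first visit, record usual weekly sessions of lower-limb, hip and core training.
2. Ask participants to keep this training stable until the week-8 test, and state this in the protocol. If the consent form or handout already says so, bring the wording into Section 9.2.
3. Add one weekly line for such sessions to the compliance chart, and add the new items to 9.3, 9.5 and 11.5.
4. In 11.1, name the analysis for Aims 3 and 4: a rank correlation between compliance and outcome change, reported unadjusted and adjusted for baseline outside training. Adjustment for training during the eight weeks should be a sensitivity analysis only. It is measured after baseline and may be prompted by the HEP, so adjusting for it could remove part of a real effect.
5. For Aims 1 and 2, keep everyone in the main test and describe changes in outside training. Repeat the test without those whose training changed, using a threshold set in advance, only as a sensitivity analysis.

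The cost is one question, eight chart lines and one covariate; at n = 28 the adjusted correlation has 28 − 3 = 25 degrees of freedom instead of 28 − 2 = 26. Self-report error will leave some confounding, and precision falls slightly. For Aims 1 and 2 the help is only partial, because retest and time effects remain without a control group.

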**12.0 Provisions to Monitor the Data to Ensure the Safety of Subjects\***

12.1 N/A

**13.0 Withdrawal of Subjects\***

13.1 Non-study related injury that affects ability to complete HEP or FSDT post intervention.

13.2 After the participant has notified any investigator that they wish no longer to continue or no longer meet the inclusion/exclusion criteria, the investigators will notify the participant that they have been

withdrawn from the study and document the nature for withdrawal and date. The participant will return the compliance sheet to the investigators.

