### **sEMG**

Data processing: Raw sEMG signals will be bandpass filtered between 10-500 Hz. The signal will be rectified, then smoothed using the Root Mean Square method with a 50ms window. The signal will be normalized to the MVIC obtained during the MVIC testing.

Data analysis: Following MVIC normalization, the mean EMG activation and peak EMG activation for each trial will be recorded. Each step-down repetition will be analyzed as a separate trial, and an average taken of all 5 trials to provide the data for each muscle pre- and post-test.

11.2 G\*power (Heinrich-Heine-University Düsseldorf, Düsseldorf, Germany) software was used to perform an a priori power analysis to determine the required N for this investigation. Data was obtained from [name] and [name] (2020), which showed a significant within-groups difference pre-exertion and five minutes post-exertion change on the FSDT ( $r = .27$ ). Pearson's coefficient was converted to Cohen's d ( $d = .56$ ). An N of 29 was calculated to achieve significant results, with beta = .80 and alpha = .05 for a two-tailed hypothesis from a repeated-measures design within groups analysis. We

assumed an attrition rate of 20% given the repeated-measures design of the investigation. Therefore, a final N of 35 will be recruited for the successful completion of this study.

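### Sections 13.1 and 13.2 do not separate stopping the exercises from leaving the study, so week-8 outcomes that could be collected are lost

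*Combined protocol and SAP*

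**What the plan says.** - **Grounds for withdrawal.** Section 13.1 lists "Non-study related injury that affects ability to complete HEP or FSDT post intervention". Section 13.2 adds participants who tell an investigator that "they wish no longer to continue or no longer meet the inclusion/exclusion criteria". Section 3.2 excludes "current knee pain or pathology in the dominant leg" and known pregnancy, so either one arising during the eight weeks would count as lost eligibility.
- **Consequence.** Section 13.2 has the participant "withdrawn from the study and document the nature for withdrawal and date". It then adds: "The participant will return the compliance sheet to the investigators". No post-test is mentioned for these people, and section 13.3 is marked not applicable.
- **Everyone else.** The end of section 9.2 schedules each participant for a follow-up FSDT and sEMG. No minimum number of the 16 sessions is required.
- **Analysis.** Section 11.1 names paired tests for FSDT and sEMG. It defines no analysis set and no handling of missing post-tests, and it names no test for the dose-response aims.
- **Attrition.** In section 11.2 the authors "assumed an attrition rate of 20% given the repeated-measures design of the investigation" and raise the sample from 29 to 35.

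**The concern.** The wording in section 13.1 joins the HEP and the FSDT with *or*. An injury that prevents the exercises but not the step-down test is therefore enough to withdraw someone from the study. Section 13.2 does not say whether a wish to stop means stopping the exercises or stopping the study. Either way, it provides only for withdrawal from the study.

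Two things are at stake:

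- **Aims 3 and 4** relate compliance to change. People who stop early are one source of low session counts. The plan recovers their dose record but not the outcome to set against it.
- **Aims 1 and 2** are single-group pre-post comparisons. No control arm offsets selective loss, and a paired test drops anyone without a post-test. If those who leave would have changed less, the remaining pairs overstate the change among all enrolled. The attrition allowance addresses precision, not this.

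**Working it through.** **1. The plan's own figures (section 11.2).** Inputs: r = 0.27, two-sided alpha 0.05, power 0.80, attrition 20%.

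- Effect size: d = 2r/√(1 − r²) = 0.54/√0.9271 = 0.56, as stated.
- Sample size: a paired t-test at d = 0.56 needs 28 pairs. A Wilcoxon signed-rank test with efficiency 3/π needs 29 (power 81.0%), as stated.
- Inflation: 29 × 1.20 = 34.8, giving 35, as stated. Losing 20% of 35 leaves 35 × 0.80 = 28 pairs, with Wilcoxon power 79.6%. Dividing instead, 29/0.80 = 36.25, gives 37.

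So the plan's own allowance corresponds to 7 people without a post-test.

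**2. Dose-response power (Aims 3 and 4).** The documents give no correlation and no test. I assume a true correlation of 0.5, roughly normal compliance and a two-sided test of the correlation at 0.05. In the extreme case the 7 lost are exactly the 7 lowest compliers.

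- Removing the lowest 20%: cut-point a = −0.842, and L = φ(a)/0.80 = 0.350. Remaining compliance variance = 1 + aL − L² = 1 − 0.295 − 0.122 = 0.583 of the full value.
- Restricted correlation = 0.5 × √0.583 / √(0.75 + 0.25 × 0.583) = 0.403.
- Power = Φ(atanh(r) × √(n − 3) − 1.96).

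| Case | r | n | Calculation | Power |
|---|---|---|---|---|
| None lost | 0.500 | 35 | 0.549 × 5.657 − 1.96 = 1.147 | 87% |
| 7 lost at random | 0.500 | 28 | 0.549 × 5 − 1.96 = 0.787 | 78% |
| 7 lowest lost | 0.403 | 28 | 0.427 × 5 − 1.96 = 0.176 | 57% |

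Of the 30-point fall, about 9 points come from how many are lost and about 21 from who is lost. A simulation with sessions uniform from 0 to 16 gives the same picture at r = 0.5: 90%, 82% and 64%. At r = 0.3 it gives 43%, 35% and 25%.

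**3. Bias in the pre-post tests (Aims 1 and 2).** Assume no true mean change, 35 enrolled and the 7 lowest on a latent tendency to stay lost. That tendency has correlation ρ with change. The expected shift in the completers' mean is about ρ × L = 0.350ρ standard deviations (SD) of change. Simulation (20,000 trials, paired t-test) gives:

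| Assumed ρ | Shift by formula | Simulated shift | Type I error |
|---|---|---|---|
| 0 | 0 | 0 | 5% |
| 0.3 | 0.105 SD | 0.11 SD | 9% |
| 0.5 | 0.175 SD | 0.17 SD | 16% |
| 0.7 | 0.245 SD | 0.24 SD | 29% |

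The documents give no value for ρ. With ρ = 0 there is no bias.

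**The case against.** The strongest case against rests on five points.

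- **Low compliance is not a ground for withdrawal.** A person who does 2 of 16 sessions and does not withdraw is still scheduled for the post-test. This stands. A reader might infer that section 13 cuts off the low-dose end, or makes the analysis completers-only. Section 9.2 does not support either: the low end is thinned.
- **A non-study injury is the cause least likely to be related to response.** This stands for section 13.1. Section 13.2 (own wish, new knee pain in the tested leg) is the firmer basis for concern about bias. An injury that stops the exercises still lowers the dose, so it matters for Aims 3 and 4.
- **Some losses cannot be avoided.** Someone who cannot do the FSDT, or who refuses further contact, has no post-test under any rule. This stands. The recoverable group is those who stop the HEP but are able and willing to be tested, and its size is unknown.
- **The aims concern healthy individuals.** A post-test in a newly painful leg may reflect the pain rather than the programme. This stands in part. Whether such data belong in the main estimate is a choice of estimand, so a sensitivity analysis is needed. It does not justify a rule that also loses people without such pain.
- **The 20% is a general allowance.** Section 11.2 does not attribute it to section 13, and nothing says that those lost are the lowest compliers. This stands; the 57% is a bound under stated assumptions, not a forecast.

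**Conclusion.** The concern holds in a limited form. Sections 13.1 and 13.2 treat stopping the programme as leaving the study and provide no post-test for people who stop. The documents never state outright that outcome collection ends. That follows from withdrawal from the study with no other provision.

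The size cannot be determined from the documents. Under the extreme assumptions (r = 0.5, all 7 lost being the lowest compliers), dose-response power is about 57%. It is 78% if the same number are lost at random, a loss that the plan already expects. For Aims 1 and 2 the shift ranges from zero when loss is unrelated to change to 0.24 SD at an assumed correlation of 0.7.

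Two stronger readings are not supported:

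- A reader might infer that the rule does bias the pre-post result in the programme's favour, for example by 35/28 − 1 = 25%. That figure requires all 7 lost to have shown exactly no change, and nothing in the documents says so.
- A reader might infer that restricting the dose range distorts the dose-response slope. Under a linear relation, selection on dose alone lowers the correlation and the power but leaves the slope unbiased.

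The change is still worth making, because a missed week-8 test cannot be recovered later.

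**What to change.** **Sections 13.1 and 13.2.** Define two separate events: stopping the HEP and withdrawing from the study. Ask anyone who stops the HEP whether they still agree to the week-8 FSDT and sEMG visit. Test those who agree and whom the investigators judge able and suitable. Whether people who now meet an exclusion criterion (new dominant-knee pain, pregnancy) are tested stays with the investigators, as does the decision on when exercise stops. No clinical rule is proposed here.

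**Section 11.1.** State that Aims 1 to 4 include everyone with a post-test, whatever their compliance. No passage excludes low compliers now, so this makes the default explicit. Add a sensitivity analysis without those who stopped the HEP or had a new injury or pain in the tested leg. Report the number without a post-test by reason, with their session counts where sheets were returned.

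**Cost.** A few sentences, and at most a few visits that are already budgeted. Section 7.1 allows 220 minutes per person; less 8 × 20 = 160 for exercise and 30 for the first visit, 30 remain for the follow-up. The estimate may be slightly less favourable.
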